2.8 Safety analyses

Safety analyses will be conducted using the safety (SAF) population. Patients will be analysed by the actual treatment they received. All the safety analyses including AEs, vital signs, Laboratory parameters, ECGs [REDACTED] will be reported for double blind treatment period as well as for the treatment withdrawal period separately.

2.8.1 Adverse events (AEs)

Treatment-emergent adverse events (TEAEs) are defined as any adverse events that develops after initiation of study treatment or any event already present that worsens following exposure to the study treatment.

If an adverse event starts at the date of week 12 visit it should be allocated to the treatment epoch and not to the treatment withdrawal epoch.

TEAEs will be summarized (number of cases as a percentage of number at risk) by treatment group separately for treatment epoch and treatment withdrawal epoch. Adverse events reported 21 days after end of study date in the scope of USM will not be included in the summary tables, but will be listed. Number and percentage of patients with TEAE will be summarized by primary system organ class and preferred term for each treatment group during the double blind Treatment epoch and during the double-blind Treatment withdrawal epoch. Severity will be classified as "mild", "moderate" and "severe". Serious TEAEs, TEAEs by maximum severity and TEAEs leading to premature discontinuation from study drug will be presented in a similar format as adverse events. Additionally, a listing of patients with TEAE will be presented. Drug abuse-related adverse events (identified using a pre-specified search criterion) will be summarized during the double-blind Treatment epoch. To assess the potential for withdrawal

effect, drug abuse-related adverse events will be summarized for the double-blind Treatment withdrawal epoch.

The following additional analysis will be performed.

- Analysis of TEAES with onset date before 25-Feb-2019

For rash adverse events, following details will be listed:

- Laterality and location of rash
- Did the subject start any new topical non-pharmaceutical products within the last 14 days prior to the start of rash?
- Topical Non-pharmaceutical Products related to the event of rash including soap, detergent, perfume, cologne and lotion.
- Were there any additional contributing factors that may have led to the rash?
- Did the dermatologist agree with the event?
- Additional investigation performed to diagnose that event: yes, no

For the legal requirements of ClinicalTrials.gov and EudraCT, two required tables on <on-treatment/treatment emergent> adverse events which are not serious adverse events with an incidence greater than X% and on <on-treatment/treatment emergent> serious adverse events and SAE suspected to be related to study treatment will be provided by system organ class and preferred term on the safety set population.

If for a same patient, several consecutive AEs (irrespective of study treatment causality, seriousness and severity) occurred with the same SOC and PT:

- a single occurrence will be counted if there is ≤ 1 day gap between the end date of the preceding AE and the start date of the consecutive AE
- more than one occurrence will be counted otherwise.

For occurrence, the presence of at least one SAE / SAE suspected to be related to study treatment / non SAE has to be checked in a block e.g., among AE's in a ≤ 1 day gap block, if at least one SAE is occurring, then one occurrence is calculated for that SAE.

The number of deaths resulting from SAEs suspected to be related to study treatment and SAEs irrespective of study treatment relationship will be provided by SOC and PT.

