- Abnormal hematology evaluation, defined as any of the following, requires temporary discontinuation of study medication and repeat within 48 hours (via central or local laboratory) and follow up until recovery to \leq grade 1 Common Terminology Criteria for Adverse Events (CTCAE). Study treatment must be permanently discontinued thereafter if hematology values are abnormal again (as defined below) after re-initiation of study treatment.
 - Platelets $<50 \times 10^9/L$
 - Absolute neutrophil count $<1.0 \times 10^9/L$
 - Hemoglobin $<80 \text{ g/L}$

If discontinuation of study treatment occurs, the patient should NOT be considered withdrawn from the study. The patient should return to the clinic as soon as possible, after discontinuation of study drug, for a study treatment discontinuation visit as detailed in [Table 6-1](#). The investigator must determine the primary reason for the patient’s premature discontinuation of study treatment and record this information in the eCRF.

Patients who discontinue study drug should be treated according to the best standard of care and be encouraged to stay in the study and continue to be followed with an abbreviated schedule of assessments as indicated in [Table 6-2](#).

The investigator must also contact the IRT to register the patient’s discontinuation from study treatment.

If study drug discontinuation occurs because treatment code has been broken, please refer to [Section 5.5.9](#).

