5.6.5 Early study termination by the sponsor

Novartis may terminate the trial for reasons related to the benefit risk assessment of treatment for participants in the study, or for regulatory or medical reasons (including slow enrollment). In the event that the study is terminated early, the Institutional Review Boards (IRBs)/Ethics Committees (ECs) will be informed and will be asked to approve the process to prematurely withdraw the participants. In general, the participant should be seen as soon as possible and assessed as a prematurely withdrawn participant from the study. The withdrawal process may include additional procedures to be followed, in order to ensure that adequate consideration is given to the protection of the participant's interests.

6 Visit schedule and assessments

[Table 6-1](#) lists all of the assessments and indicates with an "X" or "S" when the visits are performed.

Patients must be seen for all visits on the designated date or as close to it as possible. (Suggested window is +/- 3 days with the exception of V199 and V201 which must be performed no later than 13-week after the Baseline visit.)

For V199 and V201, the scheduled dates should be strictly adhered to avoid treatment exposure of more than 13 weeks after baseline visit.

The scheduled visit date should be calculated based on V101 (BL) for all visits from V101 (week 0) till V201 (week 13).

Missed or rescheduled visits should not lead to automatic discontinuation. Patients who prematurely discontinue the study treatment for any reason should be scheduled for a visit as soon as possible, at which time all of the assessments listed for the Treatment Discontinuation visit (TD) will be performed. At this visit, all dispensed investigational product should be reconciled and the adverse event and concomitant medications reconciled on the CRF. If patients then agree to continue in the study (for further safety and efficacy data collection), subsequent visits will then be according to the Abbreviated schedule of assessments for patients with study treatment discontinuation as outlined in [Table 6-2](#). Patients following the Abbreviated schedule of assessments must continue to adhere to the protocol requirements for changes to concomitant medications for neuropathic pain, rescue medication and prohibited medications.

Patients will be contacted for safety evaluations during the 30 days following the last administration of study treatment.

[figure not shown]
[figure not shown]

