9.5.2.1 Adverse events

Treatment-emergent adverse events (TEAEs) are defined as any adverse events that develops after initiation of study treatment or any event already present that worsens following exposure to the study treatment.

TEAEs will be summarized (number of cases as a percentage of number at risk) by treatment group. Number and percentage of patients with TEAE will be summarized by primary system organ class and preferred term for each treatment group during the double blind Treatment epoch and during the double-blind Treatment withdrawal epoch. Relationship to study medication will be classified as related (“probably related” and “possibly related”) and unrelated (“not related”). Severity will be classified as “mild”, “moderate” and “severe”. Serious TEAEs, drug related TEAEs, TEAEs by maximum severity and TEAEs leading to premature discontinuation from study drug will be presented in a similar format as adverse events. Additionally, a listing of patients with TEAE will be presented. Drug abuse-related adverse events (identified using a pre-specified search criterion) will be summarized during the double-blind Treatment epoch. To assess the potential for withdrawal effect, drug abuse-related adverse events will be summarized for the double-blind Treatment withdrawal epoch.

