Any change to a different standard of care medication from baseline (e.g. switch from pregabalin to gabapentin) will be treated as prohibited medication	After randomization	Discontinue study treatment

Retrieved drop-out (RDO) patients are defined as patients who discontinue study treatment and decide to remain in the study by following an abbreviated schedule of assessments. These patients must continue to adhere to protocol requirements (see respective protocol Table 6-2). The design feature of retrieved drop-outs, considered in order to minimize the occurrence of missing data on primary pain parameter, is exploited for the statistical analysis as follows:

- **Permanent discontinuation of study treatment due to AE, lack of efficacy (LoE) and use of prohibited medication:** If retrieved drop-out data are available, these will be used for analysis. If no data was retrieved after study treatment discontinuation, missing data

will be multiply imputed based on placebo arm data, i.e. “jump to reference” (J2R) assumption for the EMA401 arms, missing at random assumption for placebo arm (Carpenter, Roger, and Kenward 2013). If no RDO data was collected after study treatment permanent discontinuation, missing data will be multiply imputed based on the J2R assumption for the EMA arms and under the MAR assumption for placebo arm. Of note, alternatively one could build the imputation model based on the RDO data, however, we expect sparse RDO data which will likely hinder us to build an imputation model. More details on the imputation model are specified in Section 5.

- **Permanent discontinuation of study treatment due to other reasons than AE, LoE and use of prohibited medication (including discontinuation due to USM):** If efficacy data collected after study treatment discontinuation are available (retrieved drop-out), then the retrieved drop-out data will be excluded and missing data after study treatment discontinuation will be multiply imputed using the MAR assumption.

The multiple imputations will be carried out on the weekly mean pain score. Details on multiple imputation can be found in Section 5 of this document.

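### The TEAE definition has no end tied to last dose, so events in patients followed off drug count as treatment-epoch TEAEs in every arm

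*SAP*

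**What the plan says.** **Definition.** SAP 2.8.1 states: "Treatment-emergent adverse events (TEAEs) are defined as any adverse events that develops after initiation of study treatment or any event already present that worsens" after exposure to study treatment. Protocol 9.5.2.1 opens the same way: "Treatment-emergent adverse events (TEAEs) are defined as any adverse events that develops after initiation of study treatment". Both give a start. Neither gives an end relative to last dose or a residual-effect window.

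**Follow-up after stopping.** Protocol 5.6.2 says: "Patients who discontinue study drug should be treated according to the best standard of care and be encouraged to stay in the study". Table 6-2 sets out their abbreviated schedule. It labels the visits from Day 8 to Day 85 as Treatment epoch and marks AEs/SAEs for collection at each of them. SAP 2.5.2 recognises the group: "Retrieved drop-out (RDO) patients are defined as patients who discontinue study treatment and decide to remain in the study".

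**Tabulation.** SAP 2.8 says: "Patients will be analysed by the actual treatment they received". SAP 2.8.1 summarises TEAEs "by treatment group separately for treatment epoch and treatment withdrawal epoch". There is no off-drug category within the treatment epoch.

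**Limits that do exist.** SAP 2.8.1 keeps adverse events reported 21 days after the end-of-study date, in the scope of the urgent safety measures (USM), out of the summary tables and lists them instead. It also adds an analysis of TEAEs with onset before 25-Feb-2019. Protocol Section 6 has a period that runs from last dose, "Patients will be contacted for safety evaluations during the 30 days following the last administration of study treatment", but the TEAE definition does not use it.

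**The concern.** TEAEs are the stated measure of the safety objective (Protocol Table 2-1, SAP Table 1-1). Under this rule, a patient who takes one week of 100 mg b.i.d., stops, stays in the study and has a new event in Week 11 appears in the 100 mg b.i.d. treatment-epoch table exactly as if still on drug. A placebo patient with the same history appears under placebo.

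How much off-drug time each column holds depends on how many patients in that arm stop, when they stop, and whether they stay. If these differ between arms, part of a between-arm difference in TEAE incidence can reflect unequal off-drug follow-up. If they are similar, background events are added to all arms and can blur a dose-related signal.

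The SAP separates on-drug from off-drug data elsewhere. SAP 2.5.3 does not allow on-treatment pain scores to be averaged with retrieved drop-out scores. SAP 2.1.1 gives patients switched to placebo in the one-week withdrawal epoch their own table columns. The treatment-epoch safety tables have no matching rule, although off-drug time there can reach 11 weeks.

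**Working it through.** The documents give no figure for this point, so there is nothing to reproduce. The check traces the rule and then sizes it.

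**Step 1: do the existing limits catch the case?** Take a patient who stops at Week 4 and has a new event at Week 10, before 25-Feb-2019. Onset follows the first dose, so it is a TEAE. Table 6-2 puts the visit in the Treatment epoch. The event precedes the end-of-study date, so the 21-day exclusion does not apply. Onset is before 25-Feb-2019, so the additional analysis keeps it. Neither limit removes it.

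**Step 2: off-drug days counted for one patient.** Visit days come from Tables 6-1 and 6-2. Off-drug days = 85 − stop day; share = off-drug days / 84. The last column shows what a cut at last dose + 30 days would move out.

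| Stop visit | Stop day | Off-drug days to Day 85 | Share of 84 days | Days beyond last dose + 30 |
|---|---|---|---|---|
| Week 1 | 8 | 77 | 92% | 47 |
| Week 2 | 15 | 70 | 83% | 40 |
| Week 4 | 29 | 56 | 67% | 26 |
| Week 6 | 43 | 42 | 50% | 12 |
| Week 8 | 57 | 28 | 33% | 0 |
| Week 10 | 71 | 14 | 17% | 0 |

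**Step 3: share of an arm's follow-up.** Assume a share f of the arm stops at times uniform over 84 days and stays to Week 12. The documents do not give f.

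- All off-drug time: f × E[(84 − s)/84] = f/2, which is 5% at f = 10% and 15% at f = 30%.
- More than 30 days after last dose: f × 54² / (2 × 84²) = f × 2916/14112 = 0.207f, which is 2.1% at f = 10% and 6.2% at f = 30%.

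The second figure is what a 30-day window would change. It is about 2.4 times smaller than the first (0.5/0.207).

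**Step 4: patients per arm.** SAP Amendment 1 reports 129 randomized. At 1:1:1 that is 129/3 = 43 per arm, so one patient is 1/43 = 2.3 percentage points.

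As an illustration, suppose a share f of 10% to 30% stops at Week 4 (28 days on drug, 56 off) and stays, with a constant event hazard λ = −ln(1 − I)/84 and an assumed 12-week incidence I of 30% to 50%.

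- First TEAE while off drug: 43 × f × exp(−28λ) × [1 − exp(−56λ)]. This gives 0.8 patients (f = 10%, I = 30%) to 3.8 (f = 30%, I = 50%).
- First TEAE more than 30 days after last dose: 43 × f × exp(−58λ) × [1 − exp(−26λ)]. This gives 0.4 to 1.5 patients.

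Only the second group would leave an any-TEAE count under a 30-day window.

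**The case against.** The strongest defence is that the plan is not open-ended and the practical effect is slight. Adverse-event collection ends at the end-of-study visit (Protocol 7.1), the tables are split by epoch, and SAP 2.8.1 has both a USM exclusion and an onset-date analysis. The SAP attributes many discontinuations to the termination, and for those patients the 25-Feb-2019 analysis already removes later events. SAP 2.5.2 expects retrieved drop-out data to be sparse, so few patients may have long off-drug follow-up. Exposure duration is tabulated, and discontinuations and TEAEs are listed, so a reader can partly reconstruct timing. Counting everything is also the inclusive choice in a trial stopped for safety, and no passage justifies 30 days as an attribution window. Protocol Section 6 sets that period for safety contact only.

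Much of this stands. It limits the size and means 30 days cannot be presented as the required window. It does not supply an end tied to last dose, and listings do not replace a defined summary. Nor is inclusive counting reliably conservative, since added background events can dilute a dose difference.

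A reader might infer three stronger things that the documents do not support:

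- **That the rule works against EMA401.** Placebo follows the same rule, and grouping is by treatment actually received, so the direction is not fixed.
- **That off-drug events come largely from analgesics started after the stop.** Protocol 5.6.2 refers to best standard of care, but Section 6 and Table 6-2 footnote 2 still hold these patients to the concomitant, rescue and prohibited medication requirements. These passages must be reconciled; the counting problem exists under either.
- **That dizziness, headache and nausea are the events most affected.** No passage shows this.

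**Conclusion.** The gap is real, but it is narrower than a TEAE period with no limit at all: the period has no end anchored on the patient's last dose. For patients who stop and stay, the treatment-epoch TEAE tables mix on-drug and off-drug events in all arms, and this can inflate or dilute a dose difference.

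The effect is probably small. Under uniform stopping, about 0.21f of counted follow-up lies beyond last dose + 30 days. The Week 4 illustration puts roughly 0.4 to 1.5 patients per arm in that category. Both results rest on assumed values of f, the stop times and the background incidence, and the SAP's expectation of sparse retrieved drop-out data points to a low f. At 43 per arm, even one patient is visible at 2.3 points. The point merits a low-cost clarification. It does not show that the planned safety tables are invalid.

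**What to change.** Before database lock, add to SAP 2.8.1:

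1. An on-treatment period from first dose to last dose plus a stated number of days, with the reason for that number. The protocol's 30-day safety-contact period is one candidate; the sponsor may justify another.
2. TEAE tables by arm restricted to that period.
3. A separate post-treatment table by arm for later events in patients followed off drug.
4. Retention of the all-events table and of complete SAE and death reporting, so that late-onset events are not lost.
5. The same definition applied to the registry tables, where SAP 2.8.1 leaves on-treatment and treatment-emergent as unresolved alternatives and defines no on-treatment period.

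The cost is one definition and one extra table split, from data already collected. Separately, the sponsor should reconcile Protocol 5.6.2 with Section 6 and Table 6-2 footnote 2 on which medication requirements apply after study drug is stopped.

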7.1 Adverse events

An adverse event (AE) is any untoward medical occurrence (e.g., any unfavorable and unintended sign [including abnormal laboratory findings], symptom or disease) in a subject or clinical investigation subject *after providing written informed consent* for participation in the study until the end of study visit. Therefore, an AE may or may not be temporally or causally associated with the use of a medicinal (investigational) product.

In addition, all reports of intentional misuse and abuse of the product are also considered an adverse event irrespective if a clinical event has occurred.

The occurrence of adverse events must be sought by non-directive questioning of the patient at each visit during the study. Adverse events also may be detected when they are volunteered by the patient during or between visits or through physical examination findings, laboratory test findings, or other assessments.

Abnormal laboratory values or test results constitute adverse events only if they fulfill at least one of the following criteria:

- they induce clinical signs or symptoms,
- they are considered clinically significant,
- they require therapy.

Clinically significant abnormal laboratory values or test results must be identified through a review of values outside of normal ranges/clinically notable ranges, significant changes from baseline or the previous visit, or values which are considered to be non-typical in patient with underlying disease. Investigators have the responsibility for managing the safety of individual patient and identifying adverse events. Alert ranges for laboratory and other test abnormalities are included in [Appendix 1](#).

Adverse events must be recorded in the Adverse Events CRF under the signs, symptoms or diagnosis associated with them, accompanied by the following information:

- the severity grade
 - mild: usually transient in nature and generally not interfering with normal activities
 - moderate: sufficiently discomforting to interfere with normal activities
 - severe: prevents normal activities
- its relationship to the study treatment
 - Yes
 - No
- its duration (start and end dates) or if the event is ongoing with an outcome of not recovered/not resolved must be reported.
- whether it constitutes a serious adverse event (SAE - See [Section 7.2](#) for definition of SAE) and which seriousness criteria have been met.
- action taken regarding investigational treatment

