7.2.2 SAE reporting

To ensure patient safety, every SAE, regardless of causality, occurring after the patient has provided informed consent and until 30 days after the last study visit must be reported to Novartis safety within 24 hours of learning of its occurrence. Any SAEs experienced after the 30 day period after the last study visit should only be reported to Novartis safety if the investigator suspects a causal relationship to study treatment.

All follow-up information for the SAE including information on complications, progression of the initial SAE and recurrent episodes must be reported as follow-up to the original episode within 24 hours of the investigator receiving the follow-up information. An SAE occurring at a different time interval or otherwise considered completely unrelated to a previously reported one must be reported separately as a new event.

Information about all SAEs is collected and recorded on the Serious Adverse Event Report Form; all applicable sections of the form must be completed in order to provide a clinically thorough report. The investigator must assess the relationship of each SAE to study treatment, complete the SAE Report Form in English, and submit the completed form within 24 hours to Novartis. Detailed instructions regarding the submission process and requirements for signature are to be found in the investigator folder provided to each site.

Follow-up information is submitted as instructed in the investigator folder. Each re-occurrence, complication, or progression of the original event must be reported as a follow-up to that event regardless of when it occurs. The follow-up information should describe whether the event has resolved or continues, if and how it was treated, whether the blind was broken or not, and whether the patient continued or withdrew from study participation.

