2.8.3 Laboratory data

The summary of laboratory evaluations will be presented for three groups of laboratory tests: Hematology, Chemistry and Urinalysis.

The number and percentage of patients with newly occurring or worsening laboratory abnormalities meeting the clinically notable criteria at any post-baseline visit will be summarized by laboratory parameter. For a patient to meet the criterion of a newly occurring clinically notable value, the patient needs to have a baseline value that is not clinically notable for that parameter. For a patient to meet the criterion of a worsening clinically notable value, the patient needs to have a baseline value that is clinically notable and also have a worse post-baseline value. For patients with missing baseline value, any post-baseline notable value will be considered as newly occurring.

Incidence of newly occurring liver enzymes abnormalities and renal events will be summarized using the number and percentage of patients by treatment group. Notable laboratory values will be listed.

Laboratory assessments performed at the follow-up visits in the scope of the USM will not be included in the summaries but will be listed. That means, assessments reported 21 days after end of study date will not be included in the summary tables.

Liver function tests (LFT)

To evaluate potential drug-induced liver injury, the number and percentage of patients with newly occurring or worsening abnormalities in liver function tests at any time post-baseline will be summarized by treatment. The same approach as for notable laboratory values will be used to define newly occurring or worsening abnormalities in liver function tests.

When a criterion contains multiple laboratory parameters, the criterion will only be considered to have been met when all conditions occur at the same time (i.e., within the same sample). A case where all criteria are met at a post-baseline time point will be considered as newly occurring if the criteria are not met at baseline and will be considered as worsening if the criteria are met at baseline and at least one component is worsening from baseline irrespective of whether the other(s) are better.

Listings of patients with clinically notable LFT values will be provided.

The same analysis will be repeated for the Treatment withdrawal epoch.

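### The 21-day cut on safety follow-up is set by report date from an undefined anchor, so on-study adverse events and late SAEs could appear in listings but not in by-arm tables

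*SAP*

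**What the plan says.** **Adverse events.** SAP 2.8.1 states: "Adverse events reported 21 days after end of study date in the scope of USM will not be included in the summary tables". The sentence goes on to say that these events are listed. The same section defines a TEAE as an event that starts, or worsens, after study treatment begins, with no closing date; Protocol 9.5.2.1 does the same. SAP 2.8.1 also adds an analysis of TEAEs with onset before 25-Feb-2019, the termination date used in SAP 2.2.

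**Laboratory data.** SAP 2.8.3 first states: "Laboratory assessments performed at the follow-up visits in the scope of the USM will not be included in the summaries but will be listed". It then explains this as meaning that "assessments reported 21 days after end of study date will not be included in the summary tables". Elsewhere the section counts notable values at any visit after baseline, and liver test abnormalities at any time after baseline.

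**Collection under the protocol.** Protocol 7.1 runs the adverse event period from consent "for participation in the study until the end of study visit". Protocol 7.2.2 requires that SAEs "until 30 days after the last study visit must be reported to Novartis safety within 24 hours of learning of its occurrence". Protocol Section 6 adds: "Patients will be contacted for safety evaluations during the 30 days following the last administration of study treatment". The last laboratory sample in Table 6-1 is at Visit 201, Day 92.

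**Disclosure.** SAP Section 4 lists the changes to the protocol's analyses. It names the added TEAE analysis but not the 21-day rule.

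**The concern.** The trial was stopped under urgent safety measures, so safety is the main thing its report must show by arm. Section 4 of the SAP also removes laboratory summaries other than those of clinical abnormalities, together with shift tables and safety figures. The incidence tables for TEAEs and notable laboratory values are therefore the main by-arm safety displays left. SAP 2.8 reports safety for the treatment and withdrawal periods only, so no follow-up table picks up what the 21-day rule removes.

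A listing preserves each record but gives no incidence by arm. A rule that sorts events by the day they were reported can separate an event from the period in which it began. SAP 2.8.1.1 names raised liver enzymes, neutropenia and allergic dermatitis as potential risks; the first two are laboratory findings that extra follow-up sampling could detect.

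**Working it through.** The plan gives no figure to reproduce here. The check compares dates and then the wording. I read 21 days after as later than day 21, that is, from day 22.

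**1. SAE window (Protocol 7.2.2), if end of study date = last visit**
- The SAP cut falls at last visit + 21; the SAE window closes at last visit + 30.
- Days collected but outside the tables: 30 − 21 = 9 (days 22 to 30).
- For a patient whose last visit is V201 on Day 92: cut at 92 + 21 = Day 113; window closes at 92 + 30 = Day 122.

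**2. Contact window (Protocol Section 6), anchored at last dose**
- Let L be the days from last dose to end of study date. The cut falls L + 21 days after last dose, so the days lost are max(0, 9 − L).

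| L (days) | Days lost |
|---|---|
| 0 | 9 |
| 3 | 6 |
| 7 | 2 |
| 9 or more | 0 |

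A patient who stopped treatment early and stayed in the study for at least 9 more days loses none of this window.

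**3. Effect of the undefined anchor**
- If end of study date means 25-Feb-2019 for everyone, the cut is 25-Feb + 21 days = 18-Mar-2019.
- For a last visit k days after 25-Feb-2019 (k is negative if before), the SAE days lost are 9 + k, bounded by 0 and 30. This gives 0 at k = −9 or earlier, 9 at k = 0, and 16 at k = 7.
- Under the per-patient reading the loss is always 9. Two programmers could therefore produce different tables from the same sentence.

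**4. Report date against onset date (constructed example)**
- Onset at Week 12 (Day 85), last visit Day 92, first report on Day 114 (113 + 1).
- By onset the event is a treatment-epoch TEAE. By report date it is past Day 113 and is only listed.
- The added analysis of onsets before 25-Feb-2019 is defined by onset, so it might recover such an event. The SAP does not say that it is exempt from the 21-day rule, and it omits onsets from that date on.

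**5. The two laboratory rules**
- Rule A removes every sample taken at a USM follow-up visit, whenever it falls. Rule B removes values by a 21-day interval.
- A USM follow-up sample on day 10 after end of study is removed by A and kept by B. The text nevertheless presents B as the meaning of A.
- Both limit the any-time-after-baseline counts that the same section specifies.

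**6. What one patient is worth**
- 129 randomized 1:1:1 gives 129/3 = 43 per arm, assuming equal allocation. One patient is 1/43 = 2.3 percentage points.

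**The case against.** The strongest reply is that the rule limits extra follow-up added because of the USM and leaves ordinary safety reporting alone. On that reading, SAEs in the usual 30 days would not be touched. The phrase about the scope of the USM allows this, but the sentence does not say so.

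The word reported may also be loose. SAP 2.8.3 uses performed and reported as if they were the same, so occurring may be what was meant. That is possible, and it is a reason to write onset; the same section does write onset date in its added analysis. It can also be said that a specific display limit may qualify an open-ended definition. That is fair as a principle, but it does not settle which of the two laboratory limits applies.

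Several stronger readings are tempting, and the documents do not support them:

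- **A general 30-day safety window that the SAP shortens.** The window after the last visit covers SAEs only. The other 30-day period is for contact and starts at the last dose. The adverse event period ends at the end of study visit, and no laboratory sample is scheduled after Day 92. For non-serious events and laboratory values, 21 days is longer than scheduled collection.
- **All summary tables are affected.** The text does not say all. The registry tables and the counts of deaths from SAEs in SAP 2.8.1 state no 21-day cut, and SAP 2.8.2 lists all deaths.
- **30% of post-study events disappear.** 9/30 is a share of days. Turning it into events assumes an even spread, for which there are no data.
- **Active-arm rates are understated.** The cut applies to all arms alike, SAP Section 1 says that decisions were made before unblinding, and the documents reviewed do not say what prompted the USM.

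**Conclusion.** The point holds as a defect of specification, with consequences that cannot be counted in advance. Read literally, the rule can remove an on-study TEAE from the by-arm incidences because it was reported late, contrary to the SAP's own definition. It can also leave SAEs from 9 days of the protocol's 30-day SAE window in listings only, if end of study date is each patient's last visit and if the rule reaches ordinary SAE reporting. The laboratory section contains two rules that select different samples. The anchor is undefined, 21 days has no stated reason, and Section 4 omits the rule.

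The number of events affected and the direction of any difference between arms are unknown. No records are lost, since excluded data are listed; what is missing is the by-arm count. With about 43 patients per arm, even one or two patients would be visible in an incidence table, which justifies settling the wording before database lock.

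**What to change.** In SAP 2.8.1 and 2.8.3:

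1. Define end of study date for each patient.
2. Apply any cut by adverse event onset date and by laboratory sample date.
3. Keep SAEs within the protocol's 30-day window in the by-arm SAE tables, and give the reason for 21 days where that limit stays.
4. Replace the two laboratory sentences with one rule, and align it with the any-time-after-baseline wording.
5. State whether the registry and death tables, and the analysis of onsets before 25-Feb-2019, are subject to the cut.
6. Add one separately labelled by-arm table of adverse events and notable laboratory and liver values from the later USM follow-up.
7. Record the rule in Section 4.

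There is no need to tabulate all non-serious events to 30 days after the last visit, because the protocol does not collect them that far.

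The cost is SAP wording and one or two extra tables. These cover off-treatment time and must be labelled as such, so that they are not read together with the treatment-epoch incidences.
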